## Overview and Objectives of Study Design

**Overview:** This is a phase 2, multi-center, randomized, double-blind, placebo-controlled trial testing the efficacy of dupilumab vs. placebo in eosinophilic gastritis (EoG) with or without concurrent esophageal and/or duodenal eosinophilia. Potential participants will be screened during an 8-week screening period. An esophagogastroduodenoscopy (EGD) with biopsies will be performed to determine study eligibility, and participants will be enrolled based on the presence of active disease and their ability to meet the study inclusion and exclusion criteria. Qualifying participants will be blindly randomized 1:1 to either study drug(dupilumab) or placebo and will receive 600 mg once followed by 300 mg doses every two weeks of study treatment (for a total of 6 injections). During the treatment period, participants will be monitored for adverse events/reactions and will complete patient reported outcome metrics to track their symptoms and general wellbeing. At the end of the 12-week randomized treatment period (EOT), a repeat endoscopy with biopsies will be performed to assess the change in gastric eosinophil count from pre-to-post treatment. Participants and site study staff will remain blinded to the endoscopy biopsy results until all participants have completed the DBP EOT visit. Study participants who complete the 12-week treatment phase (whether on drug or placebo) will have the option to continue into an open-label extension (OLE) and laboratory studies and patient reported outcomes will be completed as indicated in the schedule of activities (SOA). The OLE ensures that every participant gets access to the drug and will provide data on the effect of a longer treatment period in comparison to the initial 12 weeks in the double-blind phase. A final study EGD will be performed two weeks after the last dose of the study drug. All participants will be followed for an additional 12 weeks after the last dose of study drug regardless of whether they participate in the OLE.

**Objectives:** The central hypothesis of this study is that dupilumab is safe and efficacious for reducing eosinophilia and a Th2 gene profile in EoG.

### ***Primary Objective for the Double-Blind Phase (DBP) Population***

To assess the efficacy of repeat subcutaneous (SC) doses of dupilumab, compared with placebo, to reduce eosinophilic inflammation in the gastrointestinal tract of participants with EoG with or without concurrent esophageal and/or duodenal eosinophilia involvement.

### ***Secondary Objectives for the DBP Population***

- To assess the efficacy of dupilumab compared to placebo as measured by:
  - Patient global impression of severity (PGI-S)
  - Patient global impression of change (PGI-C)
  - Proportion of participants achieving threshold response < 30 eos/hpf in 5 hpfs
  - Eosinophilic Gastritis Endoscopy Assessment (EoG-EREFS)
  - Eosinophilic Gastritis Symptom Questionnaire (EoG-SQ)
  - Comprehensive assessment of histologic features (EoG HSS)

### ***Exploratory Objectives for the DBP Population***

- To assess the efficacy of dupilumab compared to placebo as measured by:
  - Severity of Dyspepsia Assessment tool (SODA)
  - Clinician global impression of severity (CGI-S)
  - Clinician global impression of change (CGI-C)
  - Quality of Life Questionnaire (SF12, PROMIS 29, PROMIS 25)
  - EoE Endoscopic Reference Score (EREFs) (participants with esophageal involvement)
  - Blood and tissue biomarkers and gastric transcripts
  - Peripheral eosinophil counts, hemoglobin & hematocrit, total protein and albumin, total IgE, iron storage panel (iron, ferritin, total iron-binding capacity)
  - Eosinophilic Duodenitis- Endoscopic Reference Score (EoD-EREFs)

### ***Exploratory Objectives for the OLE Population***

Key Objective:

To assess the efficacy of repeat SC doses of dupilumab to reduce eosinophilic inflammation in the gastrointestinal tract of participants with EoG with or without esophageal and/or duodenal eosinophilia.

- To assess the efficacy of dupilumab as measured by:
  - Patient global impression of severity (PGI-S)
  - Patient global impression of change (PGI-C)
  - Proportion of participants achieving threshold response < 30 eos/hpf in 5 hpfs
  - Eosinophilic Gastritis Endoscopy Assessment (EoG-EREFS)
  - Eosinophilic Gastritis Symptom Questionnaire (EoG-SQ)
  - Comprehensive assessment of histologic features (EoG HSS)
- To assess the efficacy of dupilumab as measured by:
  - Severity of Dyspepsia Assessment (SODA)
  - Clinician global impression of severity (CGI-S)
  - Clinician global impression of change (CGI-C)
  - Quality of Life Questionnaire (SF12, PROMIS 29, PROMIS 25)
  - EoE Endoscopic Reference Score (EREFs) (participants with esophageal involvement)
  - Blood and tissue biomarkers and gastric transcripts
  - Peripheral eosinophil counts, hemoglobin & hematocrit, total protein and albumin, total IgE, iron storage panel (iron, ferritin, total iron-binding capacity)
  - Eosinophilic Duodenitis- Endoscopic Reference Score (EoD-EREFs)

## Safety objectives

- Incidence, occurrence, and severity of AEs/SAEs
- Systemic tolerance (safety laboratory assessments)

## Sample Size Considerations

As we recognize that not all participants may complete the study, a dropout rate of 10% is assumed for all sample size calculations provided below.

It is assumed that the true mean percent reduction from baseline in mean gastric eosinophil counts when treated with dupilumab will be at least 50%. This is a conservative estimate based on the efficacy of dupilumab in EoE patients; dupilumab reduced the mean (least square) peak esophageal eosinophil count by -94/HPF (9.5 standard error; n=23) and -7.4 (9.6 standard error; n=24) in the placebo group in a recent study of EoE13. At Week 12, dupilumab versus placebo significantly reduced peak eosinophil counts from baseline (-92.9% vs +14.2%; P<0.0001). It is also assumed that the true mean percent reduction from baseline in mean eosinophil counts for the placebo group will be at most 25% and we expect it to be much less as the placebo effect in EoE was 14% increase in eosinophil levels as noted above. Assuming a standard deviation of 25 percentage units, a sample size of 20 participants per treatment group will provide at least 80% power to detect a true absolute difference in percent reduction from baseline in mean eosinophil counts of 23% at alpha = 0.05. If we assume that the dropouts from the dupilumab arm have a mean reduction in eosinophil counts similar to those on placebo (25%) then we would expect 48% decline in eosinophil count among those in the dupilumab arm, thus we are sufficiently powered even with dropouts. A sample size of 20 per treatment group will also provide at least 80% power to detect a difference in the proportions of participants with induction of disease remission of 42 percentile points (e.g. 62% vs. 20%) at the two-sided 5% level of significance. Notably, if 2 individuals in the dupilumab arm drop out then the effective disease remission rate would be 67% among those completing the study in order to obtain a 62% overall remission rate for the dupilumab arm.

## Randomization, stratification, and blinding

Randomization will be accomplished via a central variable block randomization scheme provided by an independent statistician to the study pharmacist (or qualified designee). Block sizes will vary between 2 and 4. In addition, the randomization will be stratified based on age ( $\geq 12$  to  $< 18$  and  $\geq 18$  years) and whether the patient uses or does not use systemic corticosteroids, (e.g. prednisone at daily dosage of 5 mg or higher), swallowed glucocorticosteroids for EoG (Entocort), or other systemic immunosuppression therapy at the time of randomization. The randomization schema will ensure that potential confounding factors are equally distributed among the placebo and drug treatment groups and will eliminate 'researcher selection bias'.

The investigators, site staff other than the unblinded site pharmacist/pharmacy staff, pathologists, and study participants will all remain blinded to treatment assignment and IgE levels throughout the double blind (IgE will be analyzed after participants have completed the study). The IPM, DAIT/NIAID MO, DAIT/NIAID PM, and any other personnel designated by the sponsor ([name] as PI of the study) who have regular contact with the study site will remain blinded to all treatment assignments. Unblinding of the data will occur after initial data quality review to ensure data queries for key outcome measures.

## Definitions of Patient Populations To Be Analyzed

Patient drop out is always a concern for clinical trials as if the participants who drop out are not missing at completely random (MCAR), the results may be biased. Based on our prior study of diet and eosinophilic esophagitis, a related eosinophilic condition of the gastrointestinal tract, we expect a low rate of participant

drop out (3.9%). Missing data below 5% is considered negligible, and many studies use only the complete data 26. However, our analytic strategy will be to compare all randomized participants who receive study drug (complete V1; intent to treat sample) in the primary analyses using multiple imputation to complete case. If the results yield similar results, the complete case will be the primary report, with the imputed results in supplemental data. The per protocol population analyses will be conducted as secondary (sensitivity) analyses for all outcomes. Participants who complete the blinded phase and who do not have any major protocol deviations will be considered in the per protocol set. Examples (not all inclusive) of major protocol deviations include missing more than one dose of IP or steroid use within 30 days of endoscopy.

The primary analyses will be intention-to-treat (all participants who receive at least one dose of study drug will be included), and the per protocol population analyses will be conducted as secondary (sensitivity) analyses for all outcomes. Participants who complete the blinded phase and who do not have any major protocol deviations will be considered in the per protocol set. Examples (not all inclusive) of major protocol deviations include missing more than one dose of IP or steroid use within 30 days of endoscopy.

For the intent to treat model, it is also possible that some participants may be exposed to extended dosing due to an inability to perform the endoscopy as scheduled due to a public health emergency or illness precluding undergoing an endoscopy on schedule. If a subset of participants undergo extended dosing, we will compare individuals on study drug who had extended dosing to those who did not (sensitivity analysis) to see if the primary study outcome was substantially different based on extended dosing and will perform analyses only on those who did not undergo extended dosing to ensure results are consistent.

## Endpoints

### *Primary Endpoint*

The primary outcome measure will be the relative change in the mean of the eosinophil counts from the 5 worst microscopic fields (most eosinophil dense hpfs) in the gastric antrum and/or body. Relative change is defined as (week 12 – baseline)/baseline. Regression analyses will be performed with the primary outcome measure as the dependent variable and treatment group as the independent variable. Appropriate transformations, such as a log-transformation, may be used to satisfy the distributional assumptions prior to model fitting. If there are continued concerns about data distributions, equivalent nonparametric tests will be employed. To ensure that immunosuppression (e.g. corticosteroid, swallowed glucocorticosteroids for EoG (Entocort), or immunosuppressive agents) use does not influence results, we will also perform regression analyses with corticosteroid/immunosuppression therapy as a covariate (including considering binary (y/n), and dose (none, low, high).

### *Secondary Endpoints*

Secondary endpoints include

- 1) Absolute change in the mean of the peak eosinophil counts in the 5 most eosinophil dense HPFs in the gastric antrum and/or body.
- 2) Absolute change in PGI-S score.
- 3) PGI-C score at 12 weeks.
- 4) Proportion of participants achieving threshold response < 30 eos/hpf in all 5 hpfs.
- 5) Absolute change in endoscopic score as measured by EoG-EREFs.
- 6) Absolute change in the total EoG-SQ eDiary score.
- 7) Absolute change in proportion of days with any (1 or more) symptom as measured by the EoG-SQ eDiary.
- 8) Absolute change in histologic features measured by EoG HSS

### Hierarchical Testing structure

We will employ a hierarchical testing strategy to minimize the impact of multiple testing for the key secondary outcomes from the double blind. Thus, p-values will be reported only when prior outcomes had reached

significance ( $p \leq 0.05$ ). Once an outcome fails to reach significance the confidence intervals of the estimates will be reported.

|                      | End Points   | Order |
|----------------------|--|-------|
| Primary       | Relative change in mean of the peak gastric count                          | 1     |
| Key Secondary | Absolute change in EoG-HSS   | 2     |
|                      | Absolute change in mean of the peak gastric count                          | 3     |
|                      | Absolute change in EoG-REFS (total score – sum of antrum, body, fundus)    | 4     |
|                      | Absolute change in the total EG-SQ eDiary score                            | 5     |
|                      | Proportion achieving response (< 30 eos/hpf in all 5 hpfs)                 | 6     |
|                      | Absolute change in PGI-S score   | 7     |
|                      | PGI-C score  | 8     |
|                      | Absolute change in proportion of days of any (1 or more) symptom in EoG-SQ | 9     |

### *Exploratory Endpoints*

#### *Double-blind*

- 1) Absolute change in SODA, SF-12, PROMIS 29, PROMIS 25, and CGI-S scores
- 2) CGI-C score at 12 weeks
- 3) Absolute change in proportion of days with each individual symptom and multiple symptoms measured by the EoG-SQ eDiary.
- 4) Absolute change in each individual EoG-SQ eDiary symptom score
- 5) Induction of disease remission (percentage who achieve histological remission in the stomach as defined by peak eosinophil counts less than 30/hpf in 1, 2, 3 and 4 of the 5 hpfs identified for the primary endpoint).
- 6) For participants with esophageal involvement and/or duodenal eosinophilia involvement, absolute change in EoE HSS and EoD HSS respectively.
- 7) Absolute and relative change in blood and tissue biomarkers and gastric transcripts
- 8) Absolute and relative change in blood eosinophil count, hemoglobin, hematocrit, total protein levels, albumin, IgE, iron storage panel (iron, ferritin, total iron-binding capacity)
- 9) The association of blood and tissue biomarkers and transcripts with drug responsiveness.
- 10) Absolute changes in esophageal and duodenal peak eosinophil levels.
- 11) Absolute changes in EoE-EREFs and EoD-EREFs in participants with esophageal and/or duodenal involvement, respectively.

For double-blind endpoints above, a comparison between drug vs placebo at 12 weeks will be made.

#### *Open Label Extension*

Two time points will be evaluated for the OLE: baseline to OLE/EOT and DBP/EOT to OLE/EOT for the endpoints listed below:

#### Key Endpoint/Outcome

Relative change of the mean of the peak eosinophil counts in the 5 most eosinophil dense HPFs in the gastric antrum and/or body.

- 1) Absolute change in the mean of the peak eosinophil counts in the 5 most eosinophil dense HPFs in the gastric antrum and/or body
- 2) Absolute change in PGI-S score
- 3) PGI-C score
- 4) Proportion achieving threshold response < 30 eos/hpf in all of the 5 hpfs identified

- 5) Absolute change in endoscopic score measured by EoG-EREFS.
- 6) Absolute change in the total and each individual EoG-SQ eDiary symptom score
- 7) Absolute change in proportion of days with each individual symptom, multiple symptoms, and any (1 or more) symptom as measured by EoG-SQ eDiary
- 8) Absolute change in SODA, SF-12, PROMIS 29, PROMIS 25, and CGI-S scores.
- 9) CGI-C score
- 10) Induction of disease remission (percentage who achieve histological remission in the stomach as defined by peak eosinophil counts less than 30/hpf in 1, 2, 3 and 4 of the 5 hpfs identified for the primary endpoint).
- 11) Absolute change in EoG histology score (EoG HSS). For participants with esophageal involvement and/or duodenal eosinophilia involvement, absolute change in EoE HSS and EoD HSS, respectively.
- 12) Absolute and relative change in blood biomarkers, tissue biomarkers, and gastric transcripts
- 13) Absolute and relative change in blood eosinophil count, hemoglobin, hematocrit, total protein levels, albumin, IgE, iron storage panel (iron, ferritin, total iron-binding capacity)
- 14) The association of blood and tissue biomarkers and transcripts with drug responsiveness.
- 15) Absolute changes in esophageal and duodenal peak eosinophil levels.
- 16) Absolute changes in EoE-EREFS and EoD-EREFS in participants with esophageal and/or duodenal involvement, respectively.

### *Safety Endpoints*

All AEs will be tracked and reported. Distributions of vital sign, urinalysis, blood chemistry and hematology measures will be evaluated.

## Statistical Analyses

### *General Principles*

Statistical analyses will be reported using summary tables, figures, and data listings. Continuous variables will be summarized with counts, means, standard deviations, medians, confidence intervals, minimums, and/or maximums. Categorical variables will be summarized by counts and by percentage of patients. Formal inferential statistical analyses techniques will be discussed in subsequent sections of this SAP. Statistical testing will be performed at the two-sided 5% level of significance.

All analyses will be performed using SAS Version 9.4 or higher on a PC platform. Table, listings, and figures will be presented in Word format. Upon completion, all SAS programs will be validated by an independent programmer. In addition, all program output will undergo a senior level statistical review. The validation process will be used to confirm that statistically valid methods have been implemented and that all data manipulations and calculations are accurate. Checks will be made to ensure accuracy, consistency with this plan, consistency within tables, and consistency between tables and corresponding data listings. Upon completion of validation and quality review procedures, all documentation will be collected and filed by the project statistician or designee.

Prior to statistical analysis, quality and distribution of the data will be examined. All individuals completing study visit 1 will be included in the analysis of the primary outcome including participants receiving steroids within the last 30 days before endoscopy. The patterns of data missingness will be evaluated by reviewing patient drop out reasons and comparing baseline patient characteristics. Missing outcome data will then be imputed using multiple imputation. Factors to be considered in the multiple imputation are the prior eosinophil counts, participant clinical characteristics and longitudinal secondary outcomes. If differences occur between the results of the ITT and PP analyses, we will explore the data to understand the pattern of missingness, using tipping point analysis to understand the impact of the missing data on inference, and consider additional imputation.

## ***Major Protocol Violations***

Major protocol violations will be identified by the clinical study team and provided to Biostatistics prior to database lock. A protocol deviation is any noncompliance with the clinical trial protocol or Good Clinical Practice (GCP). The noncompliance may be either on the part of the patient, the investigator, or the study site staff. All patients with major protocol violations will be listed by study center and patient numbers. A protocol deviation committee consisting of the project manager, study principal investigator, and lead statistician will review all cases prior to unblinded. Deviations will be determined without knowledge of randomization assignment prior to database lock.

## ***Patient Enrollment and Disposition***

Patient enrollment by site will be tabulated by treatment arm and overall. Patient disposition will be summarized by treatment arm and overall. This will include number of patients screened, number of patients who were screen failures with reason, number of patients who consented, and number of patients who were randomized. The summary will include the number and percentage of patients in each of the defined analysis populations. In addition, frequency counts and percentages of patients' reported reasons for ending the study will be summarized.

A listing will be presented to describe patient study arm, date of first and last dose, date of last visit or contact, and the reason for ending the study for each patient. Listings of inclusion/exclusion criteria responses will also be provided.

## ***Description of Demographic and Baseline Characteristics***

A summary of baseline characteristics (age, sex, race, ethnicity, atopy, historical EGIDs, years since diagnosis and concomitant steroid use) and baseline measures (gastric eosinophil count, histology scores, endoscopy scores, symptom scores, blood eos counts, and PRO scores) will be presented by treatment arm.

Demographic/baseline characteristics and measures will be summarized within each treatment group using frequency and percentages for categorical variables and mean and standard deviation or median and interquartile range for continuous variables. The two treatment groups will be compared using Fisher's Exact Test for categorical variables and the nonparametric Wilcoxon Ranks Sum Test for the continuous variables. These summaries will include patients in the ITT population and PP population.

## ***Efficacy Analyses***

### **Primary Endpoint**

The primary outcome measure will be the relative change in the mean of the eosinophil counts from the 5 worst microscopic fields in the gastric antrum and/or body. Relative change is defined as (week 12 – baseline)/baseline. Regression analyses will be performed with the primary outcome measure as the dependent variable and treatment group as the independent variable. Appropriate transformations, such as a log-transformation, may be used to satisfy the distributional assumptions prior to model fitting. If there are continued concerns about data distributions, equivalent nonparametric tests will be employed. To ensure that immunosuppression (e.g. corticosteroid, swallowed glucocorticosteroids for EoG (Entocort), or immunosuppressive agents) use does not influence results, we will also perform regression analyses with corticosteroid/immunosuppression therapy as a covariate (including considering binary (y/n), and dose (none, low, high)).

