13.1. Overview

To assess the efficacy of repeat subcutaneous (SC) doses of dupilumab, compared with placebo, to reduce eosinophilic inflammation in the stomach of EG participants in a phase 2, multi-center, randomized, double-blind, placebo-controlled trial. The participants will have histologically active EG, ongoing clinical symptoms prior to enrollment and are between 18-70 years old at the time of enrollment.

This section describes the statistical methods to be used for the analysis of the data from the study. A separate Statistical Analysis Plan (SAP), which will be documented as completed prior to unblinding the study, will describe data handling and statistical analysis approaches in detail and will augment the

statistical methods described in the protocol. The SAP will detail any modifications to the analysis plan described below.

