## Introduction

The primary objective of this study is to assess the efficacy and safety of Dupilumab in the treatment of Eosinophilic Gastritis. This document outlines the statistical methods to be implemented during the analyses of data collected within the scope of Consortium of Eosinophilic Gastrointestinal Disease Researchers' Protocol CEIGR 7810 titled "A Randomized, double-blind, placebo-controlled clinical trial to evaluate the efficacy of dupilumab (anti-IL4ra) in subjects with eosinophilic gastritis". This Statistical Analysis Plan (SAP) was prepared in accordance with CEGIR 7810 protocol, V6.0, dated 12/6/2023.

The purpose of this Statistical Analysis Plan (SAP) is to provide a framework in which answers to the protocol objectives may be achieved in a statistically rigorous fashion, without bias or analytical deficiencies, following methods identified prior to database lock. Specifically, this plan has the following purposes:

- To prospectively outline the specific types of analyses and presentations of data that will form the basis for conclusions.
- To explain in detail how the data will be handled and analyzed, adhering to commonly accepted standards and practices of biostatistical analysis. Any deviations from these guidelines must be substantiated by sound statistical reasoning and documented in writing in the final clinical study report (CSR) or manuscript.

The analyses described in this analysis plan are consistent with the analyses described in the study protocol. The order may be changed for clarity. If there are discrepancies between the protocol and SAP, the SAP will serve as the definitive analysis plan.

Any analysis performed not prospectively defined in this document will be labeled as post hoc & exploratory.

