### Exploratory Endpoints

For the exploratory outcomes measured at baseline and week 12, when normality assumption holds, we will test the association between outcomes and the arms of the study using linear mixed model; otherwise generalized linear mixed effects models will be used with the appropriate distribution function. Random study site effect will be tested; if significant, it will be included in the modeling; if insignificant, the models will be simplified to linear or generalized linear models. Appropriate transformations may be used to satisfy the normality assumptions of the model, if needed. Baseline corticosteroid/immunosuppressive therapy use will be included as a covariate in the models.

Some exploratory outcomes may include measures during or at the end of OLE. For participants that continue into the open label phase of the study, we will evaluate change for two time ranges. We will examine the overall change across the study (baseline to OLE/EOT (Week 36)). Then, we will examine change during the open label phase (DBP/EOT (Week 12) to OLE/EOT (Week 36)). When evaluating these changes, analyses will be stratified by treatment status during the blinded phase of the study. Changes of the OLE endpoints will be tested against 0 using paired t tests or signed rank tests when lacking of normality. Mean change and two-sided 95% confidence intervals will be presented.

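### Do the loosely worded fallbacks for the primary endpoint (a log-transformation, then an unnamed rank test) put the primary result at risk?

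*SAP*

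**What the plan says.** The endpoint is relative change: week 12 minus baseline, divided by baseline. For the model, the SAP (Efficacy Analyses, Primary Endpoint) says: "Regression analyses will be performed with the primary outcome measure as the dependent variable and treatment group as the independent variable". Two fallbacks follow in order. The first is: "Appropriate transformations, such as a log-transformation, may be used to satisfy the distributional assumptions prior to model fitting". The second is: "If there are continued concerns about data distributions, equivalent nonparametric tests will be employed". The SAP's Endpoints section and Protocol 13.5.2 carry the same sentences.

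Other sections supply the frame:

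- Protocol 13.7 states the hypothesis in terms of the treatment coefficient from a linear model.
- SAP General Principles sets a two-sided 5% level and has data distributions examined before analysis.
- The Hierarchical Testing structure puts this endpoint first, ahead of eight key secondary tests (orders 2 to 9).
- For baseline comparisons between arms, the SAP names the "nonparametric Wilcoxon Ranks Sum Test for the continuous variables".
- For the open-label extension it says: "Changes of the OLE endpoints will be tested against 0 using paired t tests or signed rank tests when lacking of normality".

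**The concern.** Five things are missing for the primary endpoint: the form of the log, an offset for zero counts, an objective trigger for switching, the name of the rank test, and the effect estimate under each fallback. Protocol 13.1 promised that the SAP "will describe data handling and statistical analysis approaches in detail", yet on this point the SAP repeats the protocol. It is more specific for lesser analyses, naming rank tests for baseline and extension data. For protocol deviations it fixes the blinding: "Deviations will be determined without knowledge of randomization assignment prior to database lock". No such statement covers the choice of primary test.

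Two things could be at stake. The first is the reported effect. The linear model gives a difference in mean percent change, which is what the trial was powered on. A log model gives a ratio of geometric means, and a rank test gives no estimate unless one is named. The second is status. The SAP Introduction says: "Any analysis performed not prospectively defined in this document will be labeled as post hoc & exploratory". If a fallback completed later fell under that sentence, it would be unclear whether its p-value could open the hierarchy.

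**Working it through.** **The plan's own figure.** SAP Sample Size Considerations gives 20 per arm, SD 25 points, a difference of 23 points, two-sided alpha 0.05 and at least 80% power. The standardised difference is 23/25 = 0.92. The two-sample t-test has power 80.9% and the normal approximation 82.9%. The figure reproduces, and the wording of the fallbacks does not affect it.

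**Does a literal log work?** The plan's means are -50% (dupilumab) and -25% (placebo), SD 25, taken as normal.

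- Share with relative change at or below zero: Phi(50/25) = 97.7% and Phi(25/25) = 84.1%. A log of relative change itself is unusable.
- 1 + relative change = week 12/baseline. Its log fails only for a week-12 mean of zero: Phi(-50/25) = 2.3% and Phi(-75/25) = 0.1%.
- The denominator is safe, because inclusion criterion 4 requires at least 30 eos/hpf in at least 5 fields.
- A rank test on relative change equals a rank test on week 12/baseline, since one is a monotone function of the other. It needs no offset.

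**Does the choice of fill-in change the decision?** The simulation used 20 per arm, with relative change floored at -100% and 6,000 trials per scenario. Baseline was assumed to be 30 + lognormal(3.5, 0.8), which is not a document figure. The lognormal case used log SD 0.33, so that the placebo SD is 75 x sqrt(exp(0.33^2) - 1) = 25.4 points, close to the plan's 25.

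There were thirteen fill-ins. Twelve used a Shapiro-Wilk check on residuals or on pooled data (2), at 5% or 10% (2), then the log of (week 12 + o)/(baseline + o) with o = 1, 0.5 or 0.1 (3), then Wilcoxon: 2 x 2 x 3 = 12. One more went straight from a 5% residual check to Wilcoxon.

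| Scenario | Result across the 13 fill-ins |
|---|---|
| Null, -25% in both arms, normal | type I error 4.5% to 4.7% |
| Null, -25% in both arms, lognormal | type I error 4.7% to 5.1% |
| -48% vs -25%, normal | decision differs from linear model in 0.3% to 0.6% of trials |
| -48% vs -25%, lognormal | differs in 1.8% to 3.0% |
| -50% vs 0%, normal | differs in 0.0% |

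The Monte Carlo standard error of a 5% rate is sqrt(0.05 x 0.95/6000) = 0.28 points, so the null rates are consistent with 5%.

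**How often would a fallback be reached?** With a 5% residual check at -48% vs -25%, in 4.3% of trials under normality and 48.8% under the lognormal. Even where it is reached about half the time, the decision changes in at most 3.0% of trials.

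**Does the offset move the estimate?** At -50% vs -25% (normal, SD 25), the geometric mean ratio is 0.599, 0.584 and 0.559 for offsets 1, 0.5 and 0.1. That is a modest shift in a fallback estimate; the powered quantity is unaffected.

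**The case for a change.** The best counter-argument is that free choice among the tests is not harmless. In null simulations (4,000 runs, three assumed distributions), each single test held 4.2% to 5.3%, but taking the smallest of four p-values gave 6.4%, 7.5% and 8.5%. That is a worst case for selective choice. The SAP sets an ordered sequence, each step conditional on distribution, so picking the smallest p-value would breach it, and nothing in the documents suggests it was done.

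A second argument is that a large effect would make zeros common and the offset influential. At the esophageal result the plan cites (-92.9% vs +14.2%), a normal model with SD 25 puts Phi(-7.1/25) = 38.8% of dupilumab participants at zero, and the ratio moves from 0.061 (offset 1) to 0.023 (offset 0.1). These figures do not bear weight. The SD for that scenario is assumed, and flooring the distribution at -100% creates the zeros and shifts the simulated dupilumab mean to about -86%, away from the cited -92.9%. Every test was significant in every trial there, so only the estimate is in question.

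What stands is the omission itself: the SAP does not name a between-arm estimate for either fallback, and does not say that the distribution check is blinded. The post hoc label is a weaker point, because transformation and nonparametric testing are both written down in advance and in order.

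**Conclusion.** No change is needed. The gap is real but confined to the fallbacks. The default analysis is fixed: a linear regression of relative change on treatment, with its coefficient as the effect, tested at a two-sided 5% level. The word appropriate, and the log's status as an example, rule out the unworkable literal reading. The ordinary nonparametric equivalent for two arms is the Wilcoxon rank-sum, already named for baseline comparisons.

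Following the plan with any sensible rule leaves type I error at 4.5% to 5.1% and changes the decision in 0% to 3.0% of trials. This rests on 20 per arm, the plan's means and SD (or a lognormal with similar placebo SD), an assumed baseline distribution, offsets of 0.1 to 1, and a rule-based rather than result-driven switch.

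Extra wording would gain little now. Version 2.4 of the SAP was written after imputed and complete-case results had been compared (Statistical Analysis Changes From the Protocol), so a rule added at that point could only record what was used; it would not restore prespecification. Fixing a single primary test would be a legitimate preference, but the choice belongs to the sponsor and corrects no error.
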